8.2 Part B (dose expansion stage)

8.2.1 Pre-treatment evaluations

8.2.1.1 Baseline evaluations

The following must be performed/obtained between Day -28 and Cycle 1 Day 1:

- Written informed consent.

- Demographics.
- Medical history.
- Availability of historical tumour biopsy (for confirmation of mutation status).
- Height and ECOG performance status.
- Recording of symptoms.
- Review of concurrent medications.
- Echocardiogram (within 28 days of Day 1).
- Radiological imaging (within 28 days of Day 1).
- Tumour biopsy – optional.

The following must be performed between Day -7 and Cycle 1 Day 1:

- Physical examination.
- Clinical disease assessment (if applicable).
- Performance status, weight and vital signs.
- Laboratory investigations: including full blood count, APTT, PT, urea, sodium, potassium, creatinine, ALT, AST, albumin, total protein, total bilirubin, alkaline phosphatase, calcium, LDH, creatine kinase, ESR, CRP, glucose, HbA1c, troponin I, magnesium and phosphate, tumour markers (as appropriate).
- Urinalysis (bHCG).
- ECG.

Baseline imaging must document all areas of disease present (even if specific lesions are not going to be followed for response) and the measurements of all measurable lesions must be recorded clearly. Any non-measurable lesions must be stated as being present. For clinical measurements, documentation by colour photography, including a ruler to estimate the size of the lesion, is strongly recommended.

All radiological assessments must be performed between Day -28 and before starting treatment. The interval between the last anti-cancer therapy and these measurements must be at least 28 days. All clinical measurements to assess response must be done within 7 days before the patient starting treatment. Tumour lesions that are situated in a previously irradiated area can be included as measurable disease if they are clearly progressing at the time of initiating systemic therapy.

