10.3.3 Pharmacokinetics

PK parameters will be derived from sample data, including peak plasma concentration (C_{max}), time to reach C_{max} (T_{max}), elimination half-life ($T_{1/2}$), area under the curve from zero to the time of last quantifiable concentration (AUC_{0-t}) and AUC extrapolated to infinite time (AUC_{∞}). In addition, comparison between single dose and multi-dose PK parameters will be made for assessment of steady-state drug accumulation.

Bioanalysis will be performed by Covance UK. PK samples will be analysed for all patients in Part A, with a minimum of 2 patients/cohort analysis available to inform the assessment of patient safety and dose reviews.

The Correlation between the PK parameters derived and DLT or non-DLT toxicity at each dose level. Calculation of a correlation coefficient will determine the significance.

10.3.4 Response evaluation:

The best tumour response evaluation as determined radiologically or clinically will be presented as proportions. Part A and B patients undergo response assessment every 8 weeks (2 cycles), the first response assessment is therefore at 8 weeks, and they continue after that at 8 weekly intervals unless there is clinically measurable progression or toxicity. The association of the pharmacodynamics biomarkers with treatment response will be explored.

10.3.5 Expansion cohorts (Part B):

The tolerability, PD parameters and tumour response data will be evaluated as stated above for each melanoma cohort separately.

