Guidelines for evaluation of disease

Measurable and non-measurable definitions

Measurable lesion:

- A non nodal lesion that can be accurately measured in at least one dimension (longest dimension) of 10 mm with MRI or CT when the scan slice thickness is no greater than 5mm. If the slice thickness is greater than 5mm, the minimum size of a measurable lesion must be at least double the slice thickness (e.g., if the slice thickness is 10 mm, a measurable lesion must be 20 mm).
- 10 mm calliper/ruler measurement by clinical exam or medical photography.
- 20 mm by chest x-ray.

Additionally lymph nodes can be considered pathologically enlarged and measurable if 15mm in the short axis when assessed by CT or MRI (slice thickness recommended to be no more than 5mm). At baseline and follow-up, only the short axis will be measured [Eisenhauer, 2009].

Non-measurable lesion:

- All other lesions including lesions too small to be considered measurable (longest diameter <10 mm or pathological lymph nodes with 10 mm and <15 mm short axis) as well as truly non-measurable lesions, which include: leptomeningeal disease, ascites, pleural or pericardial effusions, inflammatory breast disease, lymphangitic involvement

of the skin or lung, abdominal masses/abdominal organomegaly identified by physical exam that is not measurable by reproducible imaging techniques [Eisenhauer, 2009].

- Measurable disease: The presence of at least one measurable lesion. Palpable lesions that are not measurable by radiologic or photographic evaluations may not be utilized as the only measurable lesion.
- Non-Measurable only disease: The presence of only non-measurable lesions. Note: non-measurable only disease is not allowed per protocol.

Response criteria

Evaluation of target lesions

Definitions for assessment of response for target lesion(s) are as follows:

- Complete Response (CR): Disappearance of all target lesions. Any pathological lymph nodes must be <10mm in the short axis.
- Partial Response (PR): At least a 30% decrease in the sum of the diameters of target lesions, taking as a reference, the baseline sum of the diameters (e.g. percent change from baseline).
- Stable Disease (SD): Neither sufficient shrinkage to qualify for PR nor sufficient increase to qualify for progressive disease.

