- Progressive Disease (PrD): At least a 20% increase in the sum of the diameters of target lesions, taking as a reference, the smallest sum of diameters recorded since the treatment started (e.g. percent change from nadir, where nadir is defined as the smallest sum of diameters recorded since treatment start). In addition, the sum must have an absolute increase from nadir of 5mm.
- Not Applicable (NA): No target lesions at baseline.
- Not Evaluable (NE): Cannot be classified by one of the five preceding definitions.

Note: If lymph nodes are documented as target lesions the short axis is added into the sum of the diameters (e.g. sum of diameters is the sum of the longest diameters for non-nodal lesions and the short axis for nodal lesions). When lymph nodes decrease to non-pathological size (short axis <10mm) they should still have a measurement reported in order not to overstate progression.

If at a given assessment time point all target lesions identified at baseline are not assessed, sum of the diameters cannot be calculated for purposes of assessing CR, PR, or SD, or for use as the nadir for future assessments. However, the sum of the diameters of the assessed lesions and the percent change from nadir should be calculated to ensure that progression has not been documented. If an assessment of PrD cannot be made, the response assessment should be NE.

All lesions (nodal and non-nodal) should have their measurements recorded even when very small (e.g. 2 mm). If lesions are present but too small to measure, 5 mm should be recorded and should contribute to the sum of the diameters, unless it is likely that the lesion has disappeared in which case 0 mm should be reported.

If a lesion disappears and reappears at a subsequent time point it should continue to be measured. The response at the time when the lesion reappears will depend upon the status of the other lesions. For example, if the disease had reached a CR status then PrD would be documented at the time of reappearance. However, if the response status was PR or SD, the diameter of the reappearing lesion should be added to the remaining diameters and response determined based on percent change from baseline and percent change from nadir.

Evaluation of non-target lesions

Definitions for assessment of response for non-target lesions are as follows:

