Note: Subjects with a global deterioration of health status requiring discontinuation of treatment without objective evidence of disease progression at that time should be classified as having "symptomatic deterioration." Objective response status is determined by evaluations of disease burden. Every effort should be made to document the objective progression even after discontinuation of treatment.

In some circumstances, it may be difficult to distinguish residual disease from normal tissue. When the evaluation of CR depends on this determination, it is recommended that the residual lesion be investigated (fine needle aspirate/biopsy) to confirm the CR.

Evaluation of best overall response

The best overall response is the best response recorded from the start of the treatment until disease progression/recurrence and will be determined programmatically by GSK based on the Investigators assessment of response at each time point.

To be assigned a status of SD, follow-up disease assessment must have met the SD criteria at least once after first dose at a minimum interval of 4 weeks.

If the minimum time for SD is not met, best response will depend on the subsequent assessments. For example if an assessment of PrD follows the assessment of SD and SD does not meet the minimum time requirement the best response will be PrD. Alternative subjects lost to follow-up after an SD assessment not meeting the minimum time criteria will be considered not evaluable.

Confirmation criteria (recommended):

To be assigned a status of PR or CR, a confirmatory disease assessment should be performed no less than 4 weeks (28 days) after the criteria for response are first met.

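### Appendix 5 words the progression nadir so that it omits the pre-treatment baseline, leaving target-lesion growth at the first on-treatment scan without a valid reference

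*Combined protocol and SAP*

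**What the plan says.** Under Evaluation of target lesions, Appendix 5 sets two conditions for PrD. The first is "At least a 20% increase in the sum of the diameters of target lesions" relative to the smallest sum since treatment began. The second is that "the sum must have an absolute increase from nadir of 5mm". The reference is then restated: "where nadir is defined as the smallest sum of diameters recorded since treatment start". Partial response (PR) has a different, explicit reference: "taking as a reference, the baseline sum of the diameters (e.g. percent change from baseline". SD is residual, covering whatever qualifies as neither PR nor PrD.

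On timing, sections 8.1.1.1 (Part A) and 8.2.1.1 (Part B) both state: "All radiological assessments must be performed between Day -28 and before starting treatment". Section 10.3.4 gives 8-weekly assessments and notes that "the first response assessment is therefore at 8 weeks". It reports best response as proportions, and section 10.3.5 asks for this separately in each melanoma cohort. Section 10.2 sets nine patients per cohort.

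**The concern.** The appendix names baseline where it is the intended reference (PR) and does not name it for progression. A baseline sum recorded before treatment is not a sum recorded since treatment started. An assessor who follows the definition as written therefore cannot call progression on target-lesion growth at the first on-treatment scan, however large the growth.

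Response is a secondary endpoint, summarised descriptively in small cohorts. A patient whose target lesions grew from the outset could enter the tables as SD, with a progression date that is late or missing. If some assessors follow the wording and others follow habit, the same scan could be classified in two ways within one cohort.

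**Working it through.** The plan states no figure to reproduce here. The check applies the written rule to example sums, which are assumptions because the documents contain no patient data.

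**Rule.** PrD if current sum ÷ reference ≥ 1.20 and current sum − reference ≥ 5 mm; PR if current sum ≤ 0.70 × baseline; otherwise SD (complete response does not arise in these examples).

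**Three readings of the reference**

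- A: sums since treatment start, including the current scan.
- B: only earlier sums since treatment start.
- C: baseline plus sums since treatment start.

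**First scan.** Under A the scan is its own minimum, so the ratio is 1.00 and PrD cannot be met. Under B there is no reference at all. Only C compares the scan with baseline.

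| Baseline / week 8 / week 16 (mm) | Reading A | Reading C |
|---|---|---|
| 50 / 60 / 72 | SD; then 72/60 = +20.0%, PrD | 60/50 = +20%, +10 mm: PrD at week 8 |
| 50 / 80 / 95 | SD; then 95/80 = +18.8%, SD | 80/50 = +60%: PrD at week 8 |
| 50 / 80 / 96 | SD; then 96/80 = +20.0%, PrD | +60%: PrD at week 8 |
| 50 / 100 / 119 | SD; then 119/100 = +19.0%, SD | 100/50 = +100%: PrD at week 8 |
| 50 / 55 / 61 | SD; then 61/55 = +10.9%, SD | 55/50 = +10%, SD; then 61/50 = +22%, +11 mm: PrD |
| 50 / 40 / 48 | SD; then 48/40 = +20.0%, PrD | the same |

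Reading B matches A at week 16 in every row and gives no result at week 8. The last row shows that the wording is harmless when the sum shrinks first. The second row shows the carry-over: a sum 90% above baseline (95/50) is still SD at week 16.

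**Does week-8 SD count as best response?** Sections 5.5, 8.1.2.3 and 8.2.2.2 require at least 6 weeks from first dose, and Appendix 5 requires 4. Week 8 meets both.

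**Scale in a cohort of nine.** One patient is 1/9 = 11.1% (exact 95% interval 0.3% to 48.2%). Let p be the proportion with week-8 target growth that meets PrD against baseline. The expected number affected is 9p, and the chance of at least one is 1 − (1 − p)^9. For an assumed p of 10% to 50%, this gives 0.9 to 4.5 patients and 61% to 99.8%.

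**A growth model, for illustration.** Assume a baseline sum of 60 mm, log growth over 8 weeks with mean 0 to 0.3 and SD 0.3, and 7% measurement error on each sum. The log ratio then has SD √(0.3² + 2 × 0.07²) = 0.316, and p ≈ 1 − Φ((ln 1.2 − mean)/0.316). That is about 28% at mean 0 and 65% at mean 0.3, or 2.5 to 5.8 of nine patients under C, against none under A. The model follows target sums only, so it counts patients who would be PrD anyway through new or non-target lesions. These are upper-end figures.

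**The case against.** The strongest reply is that the sentence should not be read alone.

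- **RECIST 1.1.** Appendix 5 says that progression and response follow the RECIST 1.1 definitions, and section 3.2 and section 5.5 also tie response to RECIST. This suggests that standard practice was intended. But the appendix then writes out its own operative definition and does not say which prevails.
- **Nadir as an earlier sum.** The appendix bars an incomplete sum from several uses, among them "or for use as the nadir for future assessments". This implies that a nadir precedes the scan being judged. It weakens reading A but leads to reading B, where the first scan has no reference unless baseline is admitted.
- **Early progression.** Sections 8.1.2.3 and 8.2.2.2 provide this class before two cycles are complete, when there will usually be no earlier on-treatment scan. Calling it on target growth presupposes baseline. However, it has no measurement threshold, is absent from Table i, and stops where the scheduled scan falls, at the end of two cycles.
- **Other routes.** New lesions and non-target progression give PrD under Table i whatever the target result. An unscheduled earlier scan gives week 8 a reference, but that scan meets the same gap itself.

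All of this is good evidence of intent. None of it states that nadir includes baseline.

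A reader might also infer that a program would impose the error on every patient. The text does not support that: best overall response is "determined programmatically by GSK based on the Investigators assessment of response at each time point", so the program takes investigators' calls and is not described as computing a nadir. Nor do the documents show that leaving treatment, or the Cohort 1 rescue route, would be held up. Section 6.12 lets the investigator discontinue a participant at any time for any reason, and section 6.11 allows clinical as well as radiological criteria for continuing benefit in Part A.

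**Conclusion.** The definition is defective as written and should be corrected, but this is a gap in wording with a limited reach. Followed literally, it gives no valid reference for target-lesion growth at the first on-treatment scan: the result is 0% change and SD, or undefined. The stronger statement, that such growth can never be progression and is always scored SD, goes too far. It rests on one of two literal readings and sets aside the text pointing to baseline.

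The consequence is a possible shift between SD and PrD in best response and a late or missing progression date, at 11.1 percentage points per reclassified patient in a cohort of nine. How many patients would be affected cannot be known from the documents; the counts above depend on assumed growth and on assessors applying the literal wording. PR is referenced to baseline, so first-scan CR and PR calls do not change. The primary endpoint (MTD/RP2D and safety) and the sample size are untouched. The response summaries are descriptive, and section 10.2 states that no formal hypothesis is tested.

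**What to change.** In Appendix 5, define nadir as *the smallest sum of diameters recorded at baseline or at any later assessment before the current one*, and make the preceding reference to the smallest sum since treatment started agree with it. Use the same definition in the instructions for investigators' time-point assessments and in any eCRF field that holds percent change from nadir.

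The cost is one sentence and a check of the form; no scans or patients are added. The reported SD proportion may be slightly less favourable than under the literal wording.
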